5.6.2.5. Quality of Life

Quality of life (QoL) will be defined by raw scores obtained from the QoL questionnaire (EORTC QLQ-C30), which is to be completed by all participants at each visit. Raw score at each visit, absolute and relative change from baseline score will be described in each treatment group for the 5 items of the functional scale, the QoL, the three symptom scales and the six single items. EORTC QoL scores will be compared across time in each treatment group using a mixed model for repeated measures data.

The event to be considered in further analyses is QoL deterioration, defined as a decrease in QoL score from baseline without any return to a better state during the study. A 10% decrease in total QoL score from baseline will be considered the primary threshold of interest. Other thresholds may be considered as exploratory analyses. Of note, death will also be considered as a QoL deterioration.

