15.3.3 Secondary endpoint analysis

Efficacy endpoints

All efficacy secondary endpoints will be analyzed in the ITT and PP populations.

Progression-free survival (PFS) will be analyzed as a secondary criterion of efficacy. PFS will be defined as the time from date of randomization and resistant disease or relapse or death from any cause. Any patient not known to have died at the time of analysis will be censored based on the last recorded date on which the patient was known to be alive (i.e. their status must be known at the censored date and should not be lost to follow up or unknown). PFS will be analyzed at the time of final analysis using a stratified log-rank test (stratification factor, PS). A Cox model will also be used to test the effect of treatment and will include terms for prognostic factors (PS, age and cytogenetic group).

The analysis of objective response rate (i.e. CR or PR) will be performed using logistic regression including treatment factor and PS. Secondary analysis will be performed where the logistic regression model will allow for the effect of treatment, and will also include prognostic factors as for OS and PFS. Percentage of patients with CR, CRi, CRp and PR will be calculated and associated exact 95% CIs will be presented by treatment group. Median duration of response from onset of response (RFS) will be calculated and summarized by treatment group for the subset of responders.

Absolute and relative change from baseline EORTC quality of life (QoL) questionnaire scores will be described in each treatment group. EORTC QoL questionnaire scores will be compared across time in each treatment group using a mixed model for repeated data.

Time until QoL deterioration will be defined as a decrease in QoL score from baseline without any return to a better state during the study. A threshold of 10% decrease in QoL score will be primarily used. Other thresholds may be used as exploratory analyses. Death will also be considered as a QoL deterioration. Time to QoL deterioration will be summarized using Kaplan-Meier methods and will be compared between treatment groups using a stratified log-rank test (stratification factor, PS).

Percentage of patients who need transfusions (red blood cells and/or platelets), mean number of transfusions by patient and mean number of hospitalizations (more than over 24 hours) required during the study will be described with their corresponding 95% CI in each treatment group.

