3.5. Efficacy, Pharmacokinetic, and Safety Variables

3.5.1. Efficacy Variables

The primary objective of this study is to evaluate the efficacy and tolerability of GRASPA when combined with LDAC. The primary endpoint is overall survival (OS), defined as the time elapsed between randomization and death for any cause. Patients not known to have this event are censored on the date they were last examined.

Secondary efficacy endpoints include the following:

- 1) Complete remission (CR), Complete remission with incomplete recovery (neutrophil or platelet regeneration, CRI), Partial remission (PR)
- 2) Progression-free survival (PFS) defined as the time elapsed between randomization and resistant disease or relapse or death from any cause
- 3) Relapse Free Survival defined only for patients who achieved CR or CRI as the time elapsed between date of CR/CRI and date of disease relapse or death from any cause
- 4) Percentage of patients who need transfusions (red blood cells and/or platelets), number of transfusions by patient
- 5) Patient quality of life evaluated using the EORTC QLQ-C30 version 3 scale
- 6) Number of hospitalizations (except scheduled protocol visit) required during the study

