5.2. General Statistical Methods and Data Handling

5.2.1. General Methods

All outputs will be incorporated into Microsoft Excel or Word files, sorted and labeled according to the International Conference on Harmonisation (ICH) recommendations, and formatted to the appropriate page size(s).

Tabulations will be produced for appropriate demographic, baseline, efficacy, pharmacokinetic and safety parameters. For categorical variables, summary tabulations of the number and percentage within each category (with a category for missing data) of the parameter will be presented. For continuous variables, the mean, median, standard deviation, minimum and maximum values will be presented. Time to event data will be summarized using Kaplan-Meier methodology with median time to event and associated 2-sided 95% confidence intervals, as well as percent of censored observations.

Formal statistical hypothesis testing to be performed on the primary efficacy endpoint will be conducted at the 1-sided, 0.025 level of significance. Secondary efficacy endpoints will be conducted at the 2-sided, 0.05 level of significance. Summary statistics will be presented, as well as confidence intervals on selected parameters, as described in the sections below.

Any patient not known to have had an event (death/progression) at the time of analysis will be censored based on the last recorded date on which the patient was known to be event-free.

For numeric secondary endpoints (e.g. quality of life scores) the analysis of these endpoints will be based on observed data. For repeated measures analyses using mixed models, all available data will be included in the analysis, and missing data will not be imputed.

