5.6.2.2. Progression-Free Survival (PFS)

PFS was originally defined as death due to progression in the protocol. However, to be consistent with regulatory guidance, which considers death from any cause in its definition, this endpoint was modified to be time elapsed between randomization and disease progression or death from any cause. Patients not known to have any of these events will be censored on the date they were last known to be event-free.

Progressive disease (PD) will be defined according to the section “AML-DISEASE EVALUATION” in the e-CRF as any of the following

- At least a 25% increase of BMBC compared with baseline (defined in the section “AML history / BM evaluation at baseline”, Bone Marrow Aspirate - Analyte - Blast)
- At least a 50% increase of PBBC compared with baseline
- Presence of extramedullary disease

Potential PD events presented by the patients will be reviewed and approved before database lock.

The methods for the analysis of PFS will be the same as those for OS. Specifically, PFS will be analyzed at the time of final analysis using a stratified log-rank test (stratified by PS) and displayed using Kaplan-Meier curves. Furthermore, a Cox model will also be used to test the effect of treatment and will include terms for prognostic factors (PS, age and karyotypic group).

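### The SAP names no between-arm inferential analysis of quality of life: the protocol's stratified log-rank is neither restated nor withdrawn, and the mixed model compares visits within each arm

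*SAP*

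**What the plan says.** SAP 3.5.1 lists QoL among the secondary efficacy endpoints: "Patient quality of life evaluated using the EORTC QLQ-C30 version 3 scale".

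Protocol 15.3.3 plans three things for it: a description of change from baseline by arm; a mixed model, "EORTC QoL questionnaire scores will be compared across time in each treatment group using a mixed model for repeated data"; and a time-to-event analysis with death counted as deterioration, "Time to QoL deterioration will be summarized using Kaplan-Meier methods and will be compared between treatment groups using a stratified log-rank test", the stratification factor being PS.

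SAP 5.6.2.5 keeps the description and repeats the model almost word for word: "EORTC QoL scores will be compared across time in each treatment group using a mixed model for repeated measures data". It also keeps the deterioration event, the 10% threshold and the rule for deaths. Of the analysis itself it says only this: "The event to be considered in further analyses is QoL deterioration".

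SAP 5.2.1 adds two general rules. One is a summary: "Time to event data will be summarized using Kaplan-Meier methodology with median time to event and associated 2-sided 95% confidence intervals". The other is a level: "Secondary efficacy endpoints will be conducted at the 2-sided, 0.05 level of significance". Neither names a QoL test. For progression-free survival (PFS), by contrast, SAP 5.6.2.2 is explicit: "PFS will be analyzed at the time of final analysis using a stratified log-rank test (stratified by PS"). SAP section 6, on changes to planned analyses, covers the PFS definition, the primary endpoint and the dropped interim analysis, and does not mention QoL.

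**The concern.** A randomised trial answers its question through the difference between arms. As the SAP is written, QoL yields two sets of within-arm changes and no treatment effect with a confidence interval. Section 1 of the SAP says activity will be judged on the size of effect across several endpoints taken together, and QoL cannot contribute an effect size to that judgement.

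Two risks follow. First, with twice as many patients on GRASPA, side-by-side within-arm tests are more likely to reach significance in that arm even when both arms change equally. Second, if the between-arm test, its score and its threshold are settled only after results are seen, in an open-label trial, the choice will look post hoc.

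**Working it through.** The main point is textual; the figures show its size.

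**1. Is a between-arm test named?**
- Time to QoL deterioration. Protocol 15.3.3: Kaplan-Meier and PS-stratified log-rank between arms. SAP 5.6.2.5: event, threshold and death rule, no test. SAP 5.2.1: a generic Kaplan-Meier summary and a two-sided 0.05 level. SAP section 6: nothing on QoL.
- Mixed model. Both documents compare across time in each treatment group. Neither names a treatment or treatment-by-visit term, so read literally the model estimates no treatment difference.

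**2. Within-arm tests under 2:1 allocation.** Inputs: 82 and 41 patients (Protocol 15.2, SAP 5.1). Simplification: one paired change per patient, everyone observed, same mean change d in both arms, in units of the SD of change. Then t = d × √n with n − 1 degrees of freedom.
- d = 0.25, n = 82: t = 2.264, df 81, p = 0.026.
- d = 0.25, n = 41: t = 1.601, df 40, p = 0.117.
- Smallest significant d: t(0.975, 81)/√82 = 0.220 and t(0.975, 40)/√41 = 0.316.

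Any equal change between 0.22 and 0.32 SD is therefore significant in the GRASPA arm only, although the true difference between arms is zero. The value 0.25 is an assumption chosen for illustration.

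**3. What the log-rank would deliver.** With 1:2 allocation, SE(log HR) = √(1/(D × 1/3 × 2/3)). The number of events D is not given; 90 to 123 is assumed, since death counts as an event.
- D = 90: SE = 0.2236, exp(1.96 × SE) = 1.55.
- D = 123: SE = 0.1913, factor 1.45.

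The 95% CI is the estimate divided and multiplied by that factor, so it excludes 1 only for an HR below about 0.65 (1/1.55) to 0.69 (1/1.45).

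**4. What a joint mixed model would deliver.** Assume exponential survival at the medians of 6.4 and 8.0 months in SAP section 1, so S(t) = 2^(−t/median). Half-width of the 95% CI for a mean difference = 1.96 × √(1/n1 + 1/n2).
- Everyone alive (41, 82): 0.37 SD.
- 3 months: 0.723 and 0.771 alive, or 29.6 and 63.2 patients: 0.44 SD.
- 6 months: 0.522 and 0.595 alive, or 21.4 and 48.8 patients: 0.51 SD.

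These are unadjusted, single-visit values. Baseline adjustment shrinks them by √(1 − r²). With an assumed baseline correlation r of 0.5 to 0.7, they become about 0.38 to 0.31 SD at 3 months and 0.44 to 0.36 SD at 6 months.

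**5. The threshold (minor).** SAP 5.6.2.5 applies 10% to a total score that neither document defines. The natural reading is QLQ-C30 items 29 and 30 (Protocol Appendix 4), whose raw sum runs from 2 to 14.
- Relative to baseline: 1/10 = 10.0% meets the threshold and 1/11 = 9.1% does not. One point is enough from baselines 3 to 10, and two points are needed from 11 to 14. A baseline of 2 cannot fall.
- As 10% of the range: 0.1 × 12 = 1.2, so two points are always needed.

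**The case against.** The strongest reply is that the protocol's log-rank still stands. The SAP is based on Protocol version 7, says it adds detail not given there, undertakes to outline differences, and declares none for QoL. Its reference to further analyses of the deterioration event fits that reading. This reply stands in part. A reader might infer that the SAP has dropped the test, but the documents do not show that: it is not restated, and it is not withdrawn. The table list in SAP 8.1 has only one QoL table, but that is no proof of omission. The list also lacks outputs for other planned analyses, such as the QoL mixed model itself and OS before and after the amendment, and output shells are in a separate document.

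Second, the within-arm wording is not a SAP departure; the protocol has it too. The authors may have meant a joint model, though neither document says so.

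Third, QoL carries little weight. Protocol 15.3.1 and SAP 5.1 base the decision on whether GRASPA is promising on the OS hazard ratio, and transfusions and hospitalizations are also only described by arm. The time-to-deterioration analysis overlaps OS because death is an event. All of this stands and limits the impact. It does not remove the gap, because the protocol planned a between-arm test for QoL and the SAP does not say whether it remains.

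Fourth, neither document says the arms will be contrasted by within-arm significance. The figures in step 2 of the working show a hazard, not a planned inference.

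**Conclusion.** The point holds as a matter of specification. SAP 5.6.2.5 names no inferential between-arm analysis of QoL, leaves the status of the protocol's log-rank unclear, and repeats a mixed model that, read literally, gives no treatment difference. Descriptive summaries by arm are planned, so the gap is confined to inference.

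The size is modest. The OS analysis and the decision based on it are unaffected; QoL feeds only the supportive evidence. The 0.22 to 0.32 SD band rests on a single paired change with full observation. The interval widths rest on assumed event counts, exponential survival and no baseline adjustment. They show that even a correct analysis will be imprecise, which is a reason to report an estimate with its interval.

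A reader might also infer that the deterioration rule runs backwards, since items 1 to 28 rise as patients worsen. That follows only for an unreversed sum of all 30 items. SAP 5.6.2.5 lists QoL as its own scale, so items 29 and 30 are the natural reading and the direction is then right. What remains is an undefined label.

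**What to change.** Before database lock:

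- **Time to deterioration.** In SAP 5.6.2.5 restate the protocol's Kaplan-Meier summary and PS-stratified log-rank between arms, and add a stratified hazard ratio with 95% CI. If the test is being dropped on purpose, say so in section 6.
- **Mixed model.** Replace the within-arm model with one model on both arms: treatment, visit, treatment-by-visit, baseline score and PS. Report the between-arm difference with its 95% CI. State that it describes scores while patients are alive, and read it beside the time-to-deterioration analysis, which counts death. Reconcile SAP 5.2.4, which says no covariate-adjusted analysis is planned.
- **Wording (minor).** Replace the total score by the global health status/QoL scale (items 29 and 30, higher is better). Read the 10% as relative to the patient's baseline, as the SAP's wording suggests, and keep 10% of the range as an exploratory threshold.

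The cost is SAP text and a small amount of programming, with the matching outputs. No new data or visits are needed.

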5.6.2.6. Hospitalizations

For collection of information regarding hospitalizations, the following variables will be collected at each visit:

- Hospitalization (Yes/No)
If yes,
 - mean number of hospitalizations
 - mean weekly number of hospitalizations
 - reasons for hospitalization
 - mean duration of hospitalization (days)

The duration of hospitalization will be defined in days as the following:

- If hospitalization lasts more than 24 hours, the duration=End Date - Beginning Date + 1
- If hospitalization lasts less than 24 hours, the duration=1 day

Any hospitalization occurring after a PD will not be taken into account.

The number of hospitalizations will be grouped by quarter, up to an event (PD/death) and overall, by treatment group, using descriptive statistics. The mean number of hospitalizations occurring during the study, along with a corresponding 95% CI, will be calculated.

Additionally, a special focus will be taken on hospitalization lasting more than 24 hours, and all previous variables will be described for hospitalizations lasting more than 24 hours.

5.6.3. Exploratory Endpoints

Bone marrow biopsy/aspirate will be collected at study entry and analyzed for biomarker analysis of potentially relevant biomarkers, utilizing proteomic and transcriptomic techniques. Assessments could be repeated on further bone marrow aspirate, if possible. This data will be for exploratory purposes.

The following assays will be performed:

- Mononuclear cells from bone marrow of AML patients will be assessed for Asparagine synthetase (ASNS) expression by two different methods: real-time qRT-PCR for the quantification of ASNS mRNA and westernblot for the quantification of ASNS.
- Mutational analyses and detection of gene amplification of relevant oncogenes; e.g. *FLT3*, *NPM1*, *IDH*, or *KIT*.
- Dependent upon tissue availability, immunohistochemistry (IHC), gene expression profiling and transcriptomic profiling may be performed.
- Other biomarkers deemed relevant that may emerge with new scientific data.

Cells isolated from bone marrow by ficoll will be also cultured in presence of L-asparaginase. *In-vitro* sensitivity to L-asparaginase will be assessed at ERYTECH Pharma by measuring the cytotoxicity using a colorimetric assay.

ARN and proteic extraction obtained from samples will be frozen at ERYTECH Pharma in order to perform other analyses allowing a better knowledge of mechanism of action, or new drug development.

ASNS mRNA expression at baseline will be summarized by treatment group, and select efficacy endpoints will be plotted against ASNS mRNA expression.

5.7. Pharmacokinetic Evaluations

Pharmacokinetic, pharmacodynamic and immunogenicity parameters will only be assessed on the subgroup of subjects having received GRASPA. Samples of amino acids (asparagine, aspartate, glutamine and glutamate) and whole blood asparaginase will be taken on Days 11 and 18 of the first two cycles for all patients, on Days 11 and 18 of the remaining cycles for patients included before protocol amendment and on Days 11, 13, 18 and 27 of the first two cycles for patients included after the protocol amendment. Summary of absolute values over time and summary of change from baseline values over time will be presented separately for patients recruited before and after the protocol amendment. Prior to analysis, the concentration data will be combined with concentration data collected in previous clinical studies. The model building will be conducted using NONMEM (Icon Development Solutions, [name], USA, 2009) and reported separately.

Regarding PK/PD analyses, as only 2 measurements of total blood asparaginase will be performed (D11 - 5 minutes before administration and D18), no accurate pharmacokinetic curve will be available for encapsulated asparaginase. Only those pharmacokinetic measurements which can be calculate using two timepoints will be presented.

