Pharmacokinetics and immunogenicity will only be assessed on the subgroup of subjects having received GRASPA. Samples for amino acids (asparagine, aspartate, glutamine, and glutamate), and whole blood asparaginase will be taken on Days 11, 13, 18 and 27 of the first two cycles of treatment after amendment implementation. Summary of absolute values over time (one table per parameter) and summary of change from baseline values over time (one table per parameter) and summary of change from baseline values over time (one table per parameter) and summary of change from baseline values over time (one table per parameter) will be presented separately for patients recruited before and after the protocol amendment. Whole blood L-asparaginase concentrations from this study will be evaluated using a population pharmacokinetic analysis. Prior to the analysis, the concentration data will be combined with concentration data collected in previous clinical studies. The model building will be conducted using NONMEM (Icon Development Solutions, [name], USA, 2009) and reported separately.

16. Ethics and regulatory

The Sponsor and investigators must ensure that the study will be carried out in compliance with the protocol, the principles of ICH GCP and the declaration of Helsinki (appendix 9)

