3.5.2. Pharmacokinetic Variables

Blood samples for determination of GRASPA pharmacokinetics were to be collected as outlined in the protocol. Pharmacokinetic parameters to be determined include minimum plasma concentration (C_{min}), maximum plasma concentration (C_{max}), time to maximum plasma concentration (T_{max}), the distribution rate constant (λ_{z1}), distribution half-life (dist $t_{1/2}$), elimination rate constant (λ_{z2}), terminal elimination half-life (elim $t_{1/2}$), area under the concentration versus time curve (AUC), clearance (Cl/F), and volume of distribution (β) ($Vd_{\beta/F}$).

Pharmacokinetic and pharmacodynamic endpoints include the following:

- 1) Plasma concentrations of asparagine, aspartate, glutamine, glutamate
- 2) Whole Blood L-asparaginase activity
- 3) Immunogenicity by measuring titer of anti-L-asparaginase antibodies
- 4) Biomarker cytogenetic testing (optional)
- 5) Measurement of the following parameters on harvested bone marrow tumor cells (optional):
 - a. Asparagine synthetase protein expression
 - b. Asparagine synthetase mRNA expression

c. In vitro sensitivity to L-asparaginase

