5.8.2.2. Amino-acids and total blood asparaginase

This procedure is applicable to patients under GRASPA® treatment only.

Amino acids will be described at D11 and D18 of the first two cycles of chemotherapy on all patients, at D11 and D18 of every remaining cycle for patients included before the protocol amendment and at D13 and D27 of the first two cycles for patients included after the protocol amendment:

- asparagine
- aspartate
- glutamine
- glutamate

Total blood asparaginase will be described at D11 and D18 of the first two cycles of chemotherapy on all patients, at D11 and D18 of every remaining cycle for patients included before the protocol amendment and at D13 and D27 of the first two cycles for patients included after the protocol amendment:

- Plasmatic asparaginase
- Total asparaginase
- Encapsulated asparaginase
- Free asparaginase

Encapsulated asparaginase is defined as: $\text{Total asparaginase} - \text{Plasmatic asparaginase}$.

Free asparaginase is defined as: $\text{Plasmatic asparaginase} / \text{Total asparaginase}$

For lab values reported in the format BLLQ (Below Lower Limit of Quantification), the value of limitation should be used for the purpose of including this data in the calculation of summary statistics:

Parameters	Lower limit of quantification
Asparagine	0.519 µmol/L*
Aspartate	0.987 µmol/L*
Glutamine	49.802 µmol/L*
Glutamate	10.716 µmol/L*
Plasmatic asparaginase	2.5 U/L*
Total asparaginase	75 U/L *

* These data will depend of the central laboratory, and will be confirmed before analyses.

Raw results as well as absolute and relative change from D11 will be described at each time point between treatment groups, and presented separately for patients recruited before and after the protocol amendment.

Absolute change in biological parameter between D18 and D11 will be calculated according to the formula: *Biological parameter at D18 – Biological parameter at D11*

Relative change in biological parameter between D18 and D11 will be calculated according to the formula:

$$\frac{\text{Biological parameter at D18} - \text{Biological parameter at D11}}{\text{Biological parameter at D11}} \times 100$$

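### SAP 5.7 states that asparaginase is measured only twice and limits the PK results to match, which is true only of courses sampled under the pre-amendment scheme

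*SAP*

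**What the plan says.** SAP 5.7 contains two accounts of the sampling.

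- **First paragraph.** Patients included after the amendment are sampled "on Days 11, 13, 18 and 27 of the first two cycles for patients included after the protocol amendment". The D11 and D18 scheme continues "on Days 11 and 18 of the remaining cycles for patients included before protocol amendment". The paragraph then plans descriptive output: "Summary of absolute values over time and summary of change from baseline values over time will be presented separately", the split being made at the amendment. It also plans NONMEM modelling of the concentrations pooled with earlier studies, reported separately.
- **Second paragraph.** It says that "as only 2 measurements of total blood asparaginase will be performed (D11 - 5 minutes before administration and D18"), that no accurate curve will therefore be available, and that "Only those pharmacokinetic measurements which can be calculate using two timepoints will be presented". No patient group or course is named.

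Other places bear on the same data:

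- SAP 3.5.2: "Pharmacokinetic parameters to be determined include minimum plasma concentration", followed by Cmax, Tmax, distribution and elimination rate constants and half-lives, AUC, clearance and volume of distribution.
- Protocol 15.3.3: samples "will be taken on Days 11, 13, 18 and 27 of the first two cycles of treatment after amendment implementation".
- Protocol section 8.1, Table 5: for courses 1 and 2 under version 7, one pre-dose D11 sample, four after the end of the D11 infusion (5 min, 1 h, 3 h, 6 h), then D13 (48 h), D18 (7 days) and D27 (16 days).
- SAP 5.8.2.2: total blood asparaginase and amino acids are described at D13 and D27 as well as D11 and D18, with changes from D11 at every time point. The only formula written out is headed "Absolute change in biological parameter between D18 and D11".

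**The concern.** The second paragraph of 5.7 reads as text from the pre-amendment scheme that was not updated. As it stands it is a reporting rule for the whole trial, and it cannot be followed together with 3.5.2: one section requires AUC, Cmax and two half-lives, while the other allows only what two timepoints can give. A programmer has to choose, and 5.7 is the section that governs the PK evaluation.

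Pharmacokinetics is a stated secondary objective and endpoint of the protocol (4.2 and 4.3.2), and the history of changes in Appendix 11 gives more post-infusion sampling as the purpose of the version 7 PK/PD change. If 5.7 is followed literally, the study report lacks the individual exposure parameters that this sampling can support.

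**Working it through.** **1. Reproduce the SAP's figure.** Pre-amendment scheme, per course: D11 pre-dose + D18 = 1 + 1 = 2 samples. The figure of two in SAP 5.7 is correct for that scheme.

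**2. Count the version 7 schedule (protocol Table 5), per course.**

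| Day | Samples | Number |
|---|---|---|
| D11, before administration | pre-dose | 1 |
| D11, after end of infusion | 5 min, 1 h, 3 h, 6 h | 4 |
| D13 | 48 h | 1 |
| D18 | 7 days | 1 |
| D27 | 16 days | 1 |
| **Total** | | **8** |

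Over courses 1 and 2 this is 2 × 8 = 16 samples per patient. Post-dose samples per course: 8 − 1 = 7. Under the two-sample scheme the post-dose count is 2 − 1 = 1. The net gain under version 7 is 8 − 2 = 6 samples per course.

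**3. What each scheme can identify.** SAP 3.5.2 names ten parameters: Cmin, Cmax, Tmax, two rate constants, two half-lives, AUC, clearance and volume. Two rate constants imply a biexponential curve,

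C(t) = A·exp(−αt) + B·exp(−βt),

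with four unknowns (A, α, B, β). A pre-dose sample says nothing about the curve of the dose that follows, so the number of identifiable unknowns cannot exceed the number of post-dose samples. The rank of the matrix of derivatives of C(t) with respect to the four unknowns was computed at illustrative values (A = 1, α = 0.1 per hour, B = 0.5, β = 0.003 per hour; these are assumptions, not trial data):

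- eight samples of Table 5: rank 4 of 4
- D11 pre-dose and D18 only: rank 1 of 4
- one sample on each of D11 (pre-dose), D13, D18 and D27: rank 3 of 4

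Within a course, the two-sample scheme therefore supports at most a trough-type value. It cannot give Cmax, Tmax, AUC, clearance, volume or both half-lives. The third line shows why the four post-infusion D11 samples matter: without them the two-phase curve is not determined.

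**4. What the SAP still does with the version 7 samples.**

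- D13, D18 and D27 values: summarised over time (5.7 first paragraph; Table 14.2.9.1) and described with change from D11 (5.8.2.2).
- All concentrations: available to the NONMEM model (5.7; protocol 15.3.3), in a separate report.
- Four post-infusion D11 samples per course, 4 × 2 = 8 per patient over two courses: no named summary or parameter in the SAP text.
- Reference value for change: SAP 5.8.2.2 says D11, but version 7 takes 1 + 4 = 5 samples on D11 and the SAP does not say which is meant.

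**5. Scope of the correction.** SAP 5.7 divides patients by whether they were included before or after the amendment. Protocol 15.3.3 and Table 5 apply the new schedule to courses after implementation, which may include courses of patients already enrolled. The dividing line should therefore be the sampling scheme used in a course, not the enrolment date.

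**The case against.** The strongest reply is that little is lost. The first paragraph of 5.7 keeps the summaries over time, 5.8.2.2 names D13 and D27, and the output list includes Table 14.2.9.1, an asparagine-depletion table (14.2.9.2) and a PK/PD listing (16.2.6.4). The protocol's stated analysis of whole-blood asparaginase is a population model, which the SAP keeps, and the protocol never promises a non-compartmental analysis. PK is also a secondary, descriptive endpoint with no bearing on the OS analysis or the hazard-ratio threshold.

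Much of this stands, and it rules out three stronger readings:

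- A reader might infer that six of the eight samples per course are discarded. The documents do not support that: the two-timepoint sentence restricts derived PK measurements, not the concentration summaries or the model input.
- A reader might infer from the single written formula that D13 and D27 have no planned comparison. SAP 5.8.2.2 plans change from D11 at every time point, so only the explicit formula is missing.
- A reader might infer that a pooled model cannot yield this trial's own parameters. Nothing in the documents shows this; pooling does not prevent individual estimates for these patients.

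A blanket demand for non-compartmental analysis would also be wrong, because the distribution-phase constants in 3.5.2 need a compartmental or population model.

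The reply does not remove the contradiction. Nothing limits the second paragraph of 5.7 to pre-amendment sampling, and nothing in the SAP says that the NONMEM report will supply the 3.5.2 list.

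**Conclusion.** Wrong as written. The second paragraph of SAP 5.7 conflicts with its own first paragraph, with protocol Table 5 and section 15.3.3, and with SAP 3.5.2. The loss, if it is followed literally, is that individual PK parameters for version 7 courses are not presented, and that four post-infusion D11 samples per course, in two courses, have no named analysis in the SAP outside the separately reported model. It does not touch the primary endpoint.

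This rests on Table 5 as it can be read in the protocol. Table 2 of the SAP is not readable in the text available, so whether it repeats the full schedule is not judged. The documents do not say how many patients have the full profile. The rank calculation shows which parameters are determined in principle, not how precisely. Terminal half-life also needs the later samples to stay above the quantification limit, which SAP 5.8.2.2 gives as 75 U/L for total asparaginase, subject to laboratory confirmation.

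**What to change.** - Restrict the two-timepoint sentences in SAP 5.7 to courses sampled under the pre-amendment D11 and D18 scheme, defined by scheme rather than by date of inclusion.
- For version 7 courses 1 and 2, state that the SAP 3.5.2 parameters will be presented from the full profile, and give the source of each: non-compartmental analysis for Cmax, Tmax, AUC, clearance and terminal half-life; the compartmental or NONMEM model for the distribution-phase constants. If the NONMEM report supplies any of them, say so and refer to it.
- In SAP 5.8.2.2, specify the pre-dose D11 sample as the reference, and write the change formula generally so that it visibly covers D13 and D27.

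The cost is a few sentences in the SAP before it is signed and the database is locked, the matching output shell, and a routine derivation. No additional sampling is needed and nothing changes for patients.
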